Because varenicline is expressed in the milk of animals and because of its potential for adverse effects on infant development, breastfeeding mothers will not be enrolled in the trial. Varenicline use has been associated with reduced fetal weights in animal studies. It has been assigned to Pregnancy Category C. Thus pregnant women will be excluded from this study, and pregnancy status will be biochemically verified with urine HCG measures in each participant of childbearing potential. Because of the potential benefit of smoking cessation on fetal development, pregnant women will be referred for alternative smoking cessation treatments.

B. Risks due to smoking cessation

1. Nicotine Withdrawal Symptoms. Study participants may experience nicotine withdrawal symptoms. These include anxiety, restlessness, anger, irritability, sadness, difficulty concentrating, increase in appetite, weight gain, difficulty sleeping and craving for tobacco.^{278,279} Withdrawal symptoms begin within a few hours and peak 24-48 hours after cessation and last an average of 4 weeks.²⁷⁸ Cessation of smoking can cause slowing on EEG, decreases in cortisol and catecholamine levels,²⁸⁰ sleep EEG changes, and a decline in metabolic rate. The mean heart rate decline is about 8 beats per minute, and the mean weight gain is 3-5 kg.²³¹ As with all withdrawal syndromes, the severity varies among subjects. Cessation of smoking can produce clinically significant changes in the blood levels of several medications.²⁸¹ This effect appears to be due, not to nicotine, but rather to the effects of benzopyrenes and related compounds on the P450 system. Withdrawal symptoms can also mimic, disguise, or aggravate the symptoms of other psychiatric disorders or side effects of medications.

2. Depressive Symptoms Following Smoking Cessation. We consider the likelihood of developing a severe depressive episode to be mildly elevated beyond baseline for this population during the trial, though it is not likely mediated by smoking cessation. However, our monitoring will help ensure that the development of depressive symptoms is detected at an early stage.

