Physical activity will be moderate and monitored: The risk of physical activity will be minimized by emphasizing moderate (as opposed to vigorous) activity, and by following American College of Sports Medicine guidelines regarding need for medical examination prior to beginning an exercise program.²²⁹ Participants who wish to progress to vigorous activity will be advised to obtain approval from their primary care physician. Risk of injury is further minimized by instruction on proper exercise technique, proper use of exercise equipment, the importance of warm-up and cool-down exercises, and proper stretching techniques.

Blood drawing: All phlebotomy will be performed by an experienced phlebotomist. Participants will be given information on how to contact a study clinician ([name] or [name]) if complications occur.

Extreme weight loss methods will be discouraged. The interventionist and mental health program staff will be aware of the possibility that intervention subjects could use extreme methods to lose weight. Study staff will discourage extreme calorie restriction or unbalanced diets, as these may lead to inadequate energy intake or lower than recommended intake of essential nutrients. Participants will be reminded regularly of the importance of safe weight loss. Those who have a sudden, marked weight reduction will be interviewed to determine if extreme measures have been taken. The intervention staff will be trained to detect evidence of extreme measures and will be given strategies for responding.

Minimizing risks associated with use of NRT, bupropion and varenicline. The participant's primary psychiatrist, primary care physician, [name] (safety officer) and [name] will be aware when pharmacologic treatment for smoking cessation is initiated by the prescribing psychiatrist. For example, we will discuss safety of NRT with the PCP for those who have a history of coronary artery disease or uncontrolled insulin dependent diabetes mellitus. Seizure risk from bupropion will be minimized by not having study psychiatrists prescribe bupropion to subjects with predisposing factors for seizure, including but not limited to ongoing seizure disorder, treatment with clozapine at $\geq 500\text{mg/day}$ without a therapeutic dose of an anticonvulsant medication, or head injury with loss of consciousness or other sequelae. Additionally, the risks of combining other

Protocol: Trial of Integrated Smoking Cessation, Exercise and Weight Management in SMI

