antipsychotic medications that may lower the seizure threshold and the risk of seizure with bupropion SR may be additive and will be considered by the prescribing physician. In addition, as there are choices of pharmacotherapy for smoking cessation in this study, when a participant is ready to initiate pharmacotherapy, the prescribing psychiatrist will consider the safest choice given the individual participant's profile. Weekly for the first 4 weeks and then at least twice a month the health coach will administer the Minnesota Nicotine Withdrawal Scale^{289,290} and ask participants if they have had any unanticipated visits to a health care provider, suicidality, homicidality or changes to doses of medications. These will serve as safety screens. If there are any concerning psychiatric symptoms or other issues, the health coach will follow the protocol and communicate with the intervention director and study psychiatrist, who in turn may contact the primary psychiatrist, primary care physician, and/or [name], [name] and [name].

Minimizing risks due to smoking cessation. Withdrawal symptoms are reduced by pharmacotherapeutic cessation aids (i.e., NRT, varenicline) and by participation in the behavioral intervention that helps participants strategize with coping skills. We expect exercise will also ameliorate withdrawal symptoms. Potential weight gain from smoking cessation will be addressed with the weight management aspects of the intervention that will teach methods for weight control. To minimize the risk of depressive or other psychiatric symptoms associated with smoking cessation, we emphasize that the intervention takes place at participants' own mental health programs, and all participants will be under regular, ongoing treatment with a psychiatrist and a therapist. The health coach under supervision of the intervention director, [name] and [name] will screen participants for concerning symptoms or and will follow a safety protocol including notifying the intervention director and communicating with study psychiatrists, and [name], [name] and [name]. Thus, we will believe any risks will be minimized.

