Data and safety monitoring plan: Protection of research participants begins with the eligibility criteria, which are designed to exclude individuals with serious medical conditions that would preclude their ability to safely participate in the intervention. During the study, clinical care will be provided by the participants' usual specialty mental health providers and the primary care physician, with communication with the study staff. Participants will be made aware of this delineation of responsibility. The exception to this is participants whose primary psychiatrist is the study psychiatrist. Participants in the active intervention will be monitored for psychiatric symptoms by the health coach. Recognizing the opportunity for early detection of clinical problems and the small risk of study-related morbidity, we will perform periodic safety assessments for intervention and control participants. We will inquire about cardiovascular, musculoskeletal, psychiatric and possible medication-related symptoms at 6-month intervals. We will identically apply a process to each randomized group and collect self-reported symptoms, health care utilization and records related to CVD and mental health outcomes, including emergency department use and hospitalizations, and ask standard questions regarding possible medication side effects. Clinically significant results will lead to referral to the primary care physician and/or psychiatrist. Information that comes to the attention of study personnel informally (e.g., through data collection or intervention activities at the center) may also lead to referral. Symptoms that will lead to referral include (but are not limited to) those that suggest cardiovascular disease (e.g., exertional chest pain, dyspnea, presyncope or syncope), uncontrolled hypertension, uncontrolled diabetes, complications of physical activity or psychiatric symptom exacerbation. Participants are also queried at these same time points about possible adverse events (defined below). Positive responses trigger an adverse event (AE) record, which is reviewed and classified as gastrointestinal, cardiovascular, musculoskeletal, psychiatric, or other in nature. This information is then reported to the DSMB. Similar information reported by participants at other times (e.g., during intervention classes) is noted and followed up with as needed to assure participant safety. The following constitute adverse events (AEs): heart attack, stroke, transient ischemic attack, heart failure, coronary angioplasty or bypass surgery, angina pectoris, broken bone, torn ligament, any other serious injury to the bone or muscle, seizure or hospitalization for suicidal or homicidal ideation. Evidence of the occurrence of these events is based on participant self-report that a health care professional has diagnosed the condition. We will attempt to verify the diagnosis through contact with the physician. Though not considered AEs for this study, we also will track and report the incidence of hyperlipidemia, gallbladder disease, diabetes, cancer, emergency department use and hospitalization. All other outcomes that may be construed as being an adverse consequence of study participation, such as an injury while performing a study measurement, are documented, reviewed, and followed up on as needed by a study clinician.

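### The protocol names changed blood levels of other medications as a risk of quitting, but no stated safeguard is triggered by a quit or a relapse

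*Combined protocol and SAP*

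**What the plan says.** Section 16, part B (risks due to smoking cessation), states: "Cessation of smoking can produce clinically significant changes in the blood levels of several medications". On mechanism it adds: "This effect appears to be due, not to nicotine, but rather to the effects of benzopyrenes and related compounds on the P450 system". It then warns: "Withdrawal symptoms can also mimic, disguise, or aggravate the symptoms of other psychiatric disorders or side effects of medications".

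The matching paragraph in Section 17, *Minimizing risks due to smoking cessation*, opens with withdrawal: "Withdrawal symptoms are reduced by pharmacotherapeutic cessation aids (i.e., NRT, varenicline) and by participation in the behavioral intervention". It goes on to weight gain and to depressive or other psychiatric symptoms. For the last it relies on ongoing psychiatric and therapist care and on the health coach, who "will follow a safety protocol including notifying the intervention director and communicating with study psychiatrists". Blood levels of other medications do not appear.

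The paragraph before it, on the cessation drugs, says that the primary psychiatrist, the primary care physician and the safety officer will be "aware when pharmacologic treatment for smoking cessation is initiated by the prescribing psychiatrist". It also sets a coach screen, weekly for 4 weeks and then at least twice a month. The screen uses a withdrawal scale and asks about unplanned health-care visits, suicidality, homicidality and medication dose changes. Concerns go to the intervention director and the study psychiatrist, "who in turn may contact the primary psychiatrist, primary care physician".

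Section 10 has the study physicians communicate with regular psychiatrists about the intervention while leaving regular mental health care to them. Section 15 likewise leaves usual care with the usual providers. The data and safety monitoring plan in Section 17 notes one overlap: "The exception to this is participants whose primary psychiatrist is the study psychiatrist".

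**The concern.** Stable psychotropic medication is an entry criterion (Section 5, Table 1; repeated in Section 16 under varenicline). The protocol therefore enrolls people whose doses were settled while they smoked, and then helps them stop. By its own account, stopping can shift drug levels enough to matter clinically. The source it cites is, by its title in the reference list, a case report about stopping smoking on clozapine. Section 5 does not exclude clozapine users. The clozapine conditions it and Section 17 set concern seizures and bupropion, not a quit.

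The person who can act on a changed level is the treating psychiatrist. Under the rules as written, that psychiatrist is warned that an attempt is coming but is not assured of hearing that it succeeded or later failed. What is at stake is the safety of individual participants after a quit, not the validity of the trial's result.

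**Working it through.** No figure in the plan bears on this, so the check compares texts. Each stated protection is classed by what sets it off.

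| Protection | Where | Trigger |
|---|---|---|
| Contact with treating physicians on contraindications | Section 15 | Eligibility |
| Treating psychiatrist and primary care physician aware of cessation drug | Section 17 | Start of cessation medication |
| Bupropion withheld where seizure risk is raised | Section 17 | Prescribing decision |
| Coach screen | Section 17 | Calendar |
| Escalation from the coach; onward contact discretionary | Section 17 | Concerning symptoms or other issues |
| Study clinician consults regular providers | Section 15 | A medical or psychiatric issue |
| Coach contacts primary physician (hypoglycemia and hypotension paragraph) | Section 17 | Medication change |
| Communication with regular psychiatrists | Section 10 | None stated |
| Ongoing psychiatric care | Section 17 | None (background) |
| Symptom inquiry in both arms, with referral | Section 17 | Every 6 months, or information learned informally |
| Staying in the relapse-prevention group | Section 10 | Return to smoking; leads to no prescriber contact |

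No row links a quit or a relapse to a prescriber.

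**Timing of the notice at medication start.** Table 3 starts medication in week 1 of the active group. Section 10 sets the quit date between weeks 4 and 5. The lag is 4 − 1 = 3 to 5 − 1 = 4 weeks, and longer if medication began in the motivational phase. The notice comes before the event that changes drug levels and cannot confirm it.

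**Timing of the coach screen.** The start of the first 4 weeks is not defined. If it is medication start (an assumption), weekly screening covers weeks 1 to 4 and thins at about the quit date. If it is entry to the intervention (also an assumption), someone beginning with a 4-week motivational course has used the weekly screens before the active phase. On either reading the screen follows the calendar, and its medication question is about doses already changed.

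**Symptoms as a substitute.** Section 16 itself says that withdrawal can look like, or hide, medication side effects. A symptom screen may therefore miss a changed level or misattribute it.

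**Can the size be computed?** Only a projected count of people abstinent at 18 months:

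- Per arm: 220 / 2 = 110.
- Active-arm rates stated in Section 13: 0.175 × 110 = 19.3 and 0.215 × 110 = 23.7.
- With the 60% ready-to-quit target in Section 9 in place of the 50% in Section 13 and the Table 5 footnote: 0.6 × 25% + 0.4 × 10% = 19.0%, giving 20.9; 0.6 × 30% + 0.4 × 12% = 22.8%, giving 25.1.

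The range is about 19 to 25 of 110. It leaves out everyone who quits and relapses before month 18, and it includes people on no affected drug. It does not measure the number at risk.

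**Are the data for a notice there?** Expired CO is measured weekly in the active phase, and biochemically confirmed abstinence decides entry to relapse prevention (Section 10). Medication lists are weaker. Table 2 collects them at baseline, 6, 12, 15 and 18 months, so a list may be up to about 6 months old when someone quits.

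**The case against.** The strongest reply is that the treating psychiatrist is far from uninformed. Study physicians are to communicate with regular psychiatrists about the intervention, without condition and not only at medication start. Coaches are employees of the mental health programs. Every participant is under ongoing psychiatric care. The coach screen is frequent, covers unplanned visits and dose changes, and escalates other issues as well as symptoms. A step such as telling the psychiatrist that the patient has quit also belongs naturally in the coach safety protocol or the manual of operations, neither of which was supplied.

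Most of this stands. A reader might infer from the gap that participants have no protection against altered drug levels, or that treating clinicians are kept in the dark. The documents do not support that. These safeguards may well catch a problem, and an unsupplied document may already contain the missing step. What remains is narrower. None of the stated safeguards assures the message, and the last link from study psychiatrist to primary psychiatrist is optional.

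It is also fair to object that the exception for study psychiatrists who are the treating psychiatrist sits awkwardly with Section 10, where prescribing study physicians do not deliver regular care. The exception may be rare, but where it applies the gap closes.

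**Conclusion.** The point holds as a minor, inexpensive safety improvement. The protocol calls the effect clinically significant and records the event that causes it, but states no step connecting that event to the clinician who manages the doses.

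Three stronger readings should be resisted. First, 19 to 25 participants is not the number exposed. The documents do not say how many ever quit, how many take an affected drug, or the direction and size of any change. Second, the gap does not bias the randomized comparison and touches neither the primary analysis nor power. Third, that a return to smoking would reverse the change is an inference from the stated mechanism; the protocol does not say so.

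The conclusion rests on the stated protections only. It would reduce to a missing cross-reference if the coach safety protocol already covers notice at quit and relapse.

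**What to change.** Add to *Minimizing risks due to smoking cessation* in Section 17: when an intervention participant first reaches CO-confirmed abstinence, and again when a return to smoking is found at a group, an individual session or a coach screen, the study physician notifies the treating psychiatrist, who decides whether any dose or drug level needs review. The notice lists current medications as confirmed with the participant at that contact, since the study-visit list may be out of date. The study changes no dose. No notice is needed where the study physician is the treating psychiatrist. The notice bypasses outcome assessors, so masking is kept.

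Section 17 already has a model: if a participant on a sulfonylurea markedly increases exercise, the intervention team contacts the primary care physician. If the coach safety protocol already contains the step, citing it is enough.

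The cost is a small amount of coach and physician time per event, including the medication check, with no new test. One limit remains. Relapse-prevention groups become biweekly in month 2 and then monthly, so a relapse found only through group CO could be reported up to about a month late; using the at-least-twice-monthly coach screen as well shortens that.

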17. ADEQUACY OF PROTECTION AGAINST RISKS

Recruitment and informed consent. Procedures for recruitment, consent, intervention, data collection and analysis will be reviewed and approved by the Johns Hopkins, Massachusetts General Hospital and Sheppard Pratt (Family Services Agency, Inc.) Institutional Review Boards and the DSMB. Recruitment for the study will include posters posted around each facility, flyers and brochures, and announcements and presentations at regular staff meetings at all facilities and consumer meetings (at the psychiatric day programs). We will also show an informational video. We will work with rehabilitation staff to identify potential participants by reviewing their list of program attendees with them. We plan to mail letters to potentially eligible consumers to tell them about the study. We will obtain a HIPAA waiver and work with mental health program staff to identify potential participants by reviewing their list of program attendees with them. Rehabilitation counselors and mental health clinic staff may mention the trial to their consumers. Interested individuals will be directed to contact us by phone or in person at the day program or clinic. Patients will be reminded that their continued participation in the rehabilitation program or attendance at outpatient clinic is not conditional on enrolling in the study.

Protocol: Trial of Integrated Smoking Cessation, Exercise and Weight Management in SMI

We will use a two-stage consent procedure: one consent form will be signed upon entry that covers screening and baseline data collection for the study. Another will be signed at the time of randomization. The consent forms will detail the purpose of the study, the requirements for participation, and the potential benefits and risks. We will work with the IRB to include appropriate language and protections in accordance with the data sharing policy. In consenting individuals to participate in the study, the following procedures will be used: 1) Procedures involved in the study will be fully explained to participants by study staff trained in informed consent procedures for persons with serious mental illness. 2) Participants will complete a brief test of comprehension of study procedures to demonstrate that they understand the risks and benefits of study participation and clearly consent, before consent is accepted. Any wrong answers are corrected and additional information given to clarify, until a person can easily answer all items successfully or they indicate they do not wish to continue. 3) Those agreeing to participate will sign the consent form.

Protection against risk: General

Participant safety will be closely monitored. The safety approach will be implemented similar to the investigators' other trials (e.g., ACHIEVE).^{67,69,71,106,125} We have a medical safety officer, [name], a practicing internist, who will work with Drs. [name] and [name] to promote and monitor safety throughout the study. The safety officer does not provide direct medical care and is not involved in the intervention.

Hypoglycemia, hypotension or other potential consequences of improved health behaviors or changes in medication for hypertension or diabetes mellitus will be minimized by having the intervention team communicate closely with the primary care physician and mental health program staff about medication changes, exercise participation and coordinate assistance for participants with blood sugar monitoring. For example, if an active intervention group participant is taking a sulfonylurea and has significantly increased exercise frequency, the intervention team will communicate with the primary care physician and suggest a glucose-lowering agent that would have lower risk of hypoglycemia, such as metformin. The health coach will also communicate with the primary physician after medication changes.

Physical activity will be moderate and monitored: The risk of physical activity will be minimized by emphasizing moderate (as opposed to vigorous) activity, and by following American College of Sports Medicine guidelines regarding need for medical examination prior to beginning an exercise program.²²⁹ Participants who wish to progress to vigorous activity will be advised to obtain approval from their primary care physician. Risk of injury is further minimized by instruction on proper exercise technique, proper use of exercise equipment, the importance of warm-up and cool-down exercises, and proper stretching techniques.

Blood drawing: All phlebotomy will be performed by an experienced phlebotomist. Participants will be given information on how to contact a study clinician ([name] or [name]) if complications occur.

Extreme weight loss methods will be discouraged. The interventionist and mental health program staff will be aware of the possibility that intervention subjects could use extreme methods to lose weight. Study staff will discourage extreme calorie restriction or unbalanced diets, as these may lead to inadequate energy intake or lower than recommended intake of essential nutrients. Participants will be reminded regularly of the importance of safe weight loss. Those who have a sudden, marked weight reduction will be interviewed to determine if extreme measures have been taken. The intervention staff will be trained to detect evidence of extreme measures and will be given strategies for responding.

Minimizing risks associated with use of NRT, bupropion and varenicline. The participant's primary psychiatrist, primary care physician, [name] (safety officer) and [name] will be aware when pharmacologic treatment for smoking cessation is initiated by the prescribing psychiatrist. For example, we will discuss safety of NRT with the PCP for those who have a history of coronary artery disease or uncontrolled insulin dependent diabetes mellitus. Seizure risk from bupropion will be minimized by not having study psychiatrists prescribe bupropion to subjects with predisposing factors for seizure, including but not limited to ongoing seizure disorder, treatment with clozapine at $\geq 500\text{mg/day}$ without a therapeutic dose of an anticonvulsant medication, or head injury with loss of consciousness or other sequelae. Additionally, the risks of combining other

Protocol: Trial of Integrated Smoking Cessation, Exercise and Weight Management in SMI

antipsychotic medications that may lower the seizure threshold and the risk of seizure with bupropion SR may be additive and will be considered by the prescribing physician. In addition, as there are choices of pharmacotherapy for smoking cessation in this study, when a participant is ready to initiate pharmacotherapy, the prescribing psychiatrist will consider the safest choice given the individual participant's profile. Weekly for the first 4 weeks and then at least twice a month the health coach will administer the Minnesota Nicotine Withdrawal Scale^{289,290} and ask participants if they have had any unanticipated visits to a health care provider, suicidality, homicidality or changes to doses of medications. These will serve as safety screens. If there are any concerning psychiatric symptoms or other issues, the health coach will follow the protocol and communicate with the intervention director and study psychiatrist, who in turn may contact the primary psychiatrist, primary care physician, and/or [name], [name] and [name].

Minimizing risks due to smoking cessation. Withdrawal symptoms are reduced by pharmacotherapeutic cessation aids (i.e., NRT, varenicline) and by participation in the behavioral intervention that helps participants strategize with coping skills. We expect exercise will also ameliorate withdrawal symptoms. Potential weight gain from smoking cessation will be addressed with the weight management aspects of the intervention that will teach methods for weight control. To minimize the risk of depressive or other psychiatric symptoms associated with smoking cessation, we emphasize that the intervention takes place at participants' own mental health programs, and all participants will be under regular, ongoing treatment with a psychiatrist and a therapist. The health coach under supervision of the intervention director, [name] and [name] will screen participants for concerning symptoms or and will follow a safety protocol including notifying the intervention director and communicating with study psychiatrists, and [name], [name] and [name]. Thus, we will believe any risks will be minimized.

Breach of confidentiality: All participant information will be considered confidential. This confidentiality will be assured through several mechanisms. Each participant will be assigned an anonymous study ID, which will be used on all study forms; all study forms and paper records that contain participant information will be kept in secured, locked areas when not in use. Such materials, when in use, will be kept away from public scrutiny. Forms that need to be discarded will be destroyed. Access to participant information will be restricted to authorized personnel. For computerized study data, access will be password protected. When the study database is ready for analysis, it will not contain identities of participants. During data collection, data collection forms will be stored in locked areas with access only by authorized personnel. Finally, neither the mental health programs nor participants will be identified by name in any publications. Data will not be presented in such a way that the identity of individual participants can be inferred.

Participant reimbursement: Participant reimbursement for data collection for all participants is estimated at \$115 total for completing all data collection visits, divided over each visit. Active intervention participants will receive small incentives for group and individual session attendance and for low smokelyzer readings. These will consist of earning points that may be traded in for small gifts, or earning up to \$3 for session attendance or smoking abstinence. A participant in the active intervention arm could earn up to \$200 over the course of the 18-month study for intervention participation.

Potential benefits of the proposed research to the subjects and others: Potential benefits to the study participants who receive intervention include improved health behaviors and improved cardiovascular risk profiles. All participants receive blood pressure and laboratory test results. Potential benefits to others include the possibility that the research will lead to the dissemination of effective interventions to decrease tobacco dependence and improve overall cardiovascular health in persons with serious mental illness.

Importance of knowledge to be gained: Persons with serious mental illness have high burdens of each major cardiovascular risk behavior, yet persons with SMI have been systematically excluded from interventions to decrease cardiovascular risk. If successful, this proposed integrated smoking cessation, weight management and exercise intervention could be disseminated widely. The minimal health risks to participants are offset by the potential benefits to participants and to the greater population with chronic mental illness.

Data and safety monitoring plan: Protection of research participants begins with the eligibility criteria, which are designed to exclude individuals with serious medical conditions that would preclude their ability to safely participate in the intervention. During the study, clinical care will be provided by the participants' usual specialty mental health providers and the primary care physician, with communication with the study staff. Participants will be made aware of this delineation of responsibility. The exception to this is participants whose primary psychiatrist is the study psychiatrist. Participants in the active intervention will be monitored for psychiatric symptoms by the health coach. Recognizing the opportunity for early detection of clinical problems and the small risk of study-related morbidity, we will perform periodic safety assessments for intervention and control participants. We will inquire about cardiovascular, musculoskeletal, psychiatric and possible medication-related symptoms at 6-month intervals. We will identically apply a process to each randomized group and collect self-reported symptoms, health care utilization and records related to CVD and mental health outcomes, including emergency department use and hospitalizations, and ask standard questions regarding possible medication side effects. Clinically significant results will lead to referral to the primary care physician and/or psychiatrist. Information that comes to the attention of study personnel informally (e.g., through data collection or intervention activities at the center) may also lead to referral. Symptoms that will lead to referral include (but are not limited to) those that suggest cardiovascular disease (e.g., exertional chest pain, dyspnea, presyncope or syncope), uncontrolled hypertension, uncontrolled diabetes, complications of physical activity or psychiatric symptom exacerbation. Participants are also queried at these same time points about possible adverse events (defined below). Positive responses trigger an adverse event (AE) record, which is reviewed and classified as gastrointestinal, cardiovascular, musculoskeletal, psychiatric, or other in nature. This information is then reported to the DSMB. Similar information reported by participants at other times (e.g., during intervention classes) is noted and followed up with as needed to assure participant safety. The following constitute adverse events (AEs): heart attack, stroke, transient ischemic attack, heart failure, coronary angioplasty or bypass surgery, angina pectoris, broken bone, torn ligament, any other serious injury to the bone or muscle, seizure or hospitalization for suicidal or homicidal ideation. Evidence of the occurrence of these events is based on participant self-report that a health care professional has diagnosed the condition. We will attempt to verify the diagnosis through contact with the physician. Though not considered AEs for this study, we also will track and report the incidence of hyperlipidemia, gallbladder disease, diabetes, cancer, emergency department use and hospitalization. All other outcomes that may be construed as being an adverse consequence of study participation, such as an injury while performing a study measurement, are documented, reviewed, and followed up on as needed by a study clinician.

The Data and Safety Monitoring Board will meet at least twice a year during the study. The DSMB members are clinical research scientists not otherwise connected to the study whose expertise includes biostatistics, CVD prevention, mental health and clinical trials. The committee will review the protocol before the start of fieldwork. Adverse events will be reviewed initially by [name], [name] and [name] and then reported locally to the IRB, the DSMB and the NIH project office according to prevailing policies of these review bodies. This plan should ensure participant safety.

